## SYNOPSIS

Clinical Trial Title: A multicenter open label uncontrolled study of the long term safety and efficacy of calcitriol 3 mcg/g ointment applied twice daily for 26 weeks in pediatric subjects (2 to 16 years and 11 months of age) with mild to moderate plaque psoriasis	
Short Title: Long term safety and efficacy study of calcitriol 3 mcg/g ointment in pediatric subjects with plaque psoriasis	
Clinical Trial phase:	Clinical Trial Population:
IV (III*) * for non US regions	Plaque psoriasis in pediatric subjects
Clinical Trial objectives:	To evaluate the safety of up to 26 weeks of treatment with calcitriol 3 mcg/g ointment when used twice daily, without occlusion, to treat pediatric subjects (2 to 16 years and 11 months, Version R03) with plaque psoriasis.  As a secondary objective, calcitriol plasma concentrations will be assessed at several time points throughout the study duration in a subset of children 2 to 6 years and 11 months old.
Clinical Trial design:	Multicenter, open-label uncontrolled study.
Total number of subjects (Planned):	As a screen failure rate of approximately 40 percent is expected, screening of approximately 167 subjects is planned in order to achieve the target of 100 subjects enrolled into the study.  PK investigations will be conducted in a subset of approximately 9 subjects aged between 2 to 6 years and 11 months old.
Number of clinical trial centers (Planned):	Approximately 30 study centers
Region(s) / country(ies) involved (Planned):	United States, Canada, and Europe
Clinical trial duration:	The planned clinical trial duration (from FSI to LSO) is approximately 40 months.  The planned duration of recruitment (i.e. from FSI to LSI) is approximately 34 months.
Duration of subject participation:	Clinical trial participation for each subject is approximately 32 weeks.
Key Inclusion criteria	Male or female 2 to 16 years and 11 months of age (Version R03).  Specific for PK: Pediatric subjects 2 to 6 years and 11 months of age (inclusive at Screening) and with a minimum 3% BSA involvement.  Clinical diagnosis of stable mild to moderate plaque type psoriasis. Subjects with an IGA score of 2 or 3 at Screening and Baseline.

Key Exclusion criteria	
Subjects with guttate psoriasis, pustular psoriasis, erythrodermic psoriasis or active infection (i.e., an infection associated with fever, swollen lymph nodes, and/or signs of localized inflammation of tissue and/or joints). Note: allergic or vasomotor rhinitis is not exclusionary.
 
Subject has hypercalcemia (serum albumin-adjusted calcium level above the upper normal range) at Screening.
 
Subjects with known or suspected disorders of calcium metabolism.
 
Subjects with liver dysfunction, defined as laboratory AST or ALT >2x ULN or total bilirubin >1.5x ULN.
 
Subjects with creatinine clearance <85 mL/min per 1.73 m^2 at Screening.
 
The subject has urinary calcium:creatinine ratio above the upper normal range at Screening.
 
The subject has a history or signs and symptoms of urolithiasis.
 
Subject has secondary hyperparathyroidism or PTH above upper limit of normal at Screening.
 
Subjects with underlying systemic or other dermatological conditions that require the use of systemic supplements of calcium or vitamin D. (Subjects taking oral calcium and vitamin D for prophylactic purposes must be on a stable dose for at least 4 weeks prior to screening and are not to exceed the Recommended Daily Allowance for calcium (1,300 mg for subjects aged 12-16 years and 11 months and 1,000 mg for subjects less than 12 years) or Vitamin D (600 IU).
 
The Subject has Vitamin D deficiency (25(OH)D <20 ng/mL) at Screening (Note: Subjects with 25(OH)D <20 ng/mL at screening, may undergo re-screening after at least 4 weeks of Vitamin D deficiency treatment to determine eligibility).

Investigational product:	
Name:	Vectical®/Silkis™ ointment
Internal code:	CD2027
Pharmaceutical form:	ointment
Strength/Concentration:	Calcitriol 3 mcg/g
Dosage (total daily dose):	Maximum of 0.5 g/kg of body weight or 28 grams daily (whichever is the lower)
Route:	Topical to psoriatic skin
Duration of administration:	26 weeks
Dose regimen:	Twice daily application (morning and evening)
Location of treated area:	Psoriatic skin (excluding face and scalp)

 <http://ods.od.nih.gov/factsheets/Calcium-HealthProfessional/>, National Institutes of Health Office of Dietary Supplements, Strengthening Knowledge and Understanding of Dietary Supplements

Comparator product:	Not Applicable
Name:	
Internal code:	
Pharmaceutical form:	
[Strength/Concentration]:	
Dosage (total daily dose):	
Route:	
Duration of administration:	
Dose regimen:	
Location of treated area:	
Efficacy endpoints:	Percentage of subjects with an IGA Score of 0 (clear) or 1 (almost clear). Change from Baseline in Pruritus. Change from Baseline in %BSA.
Safety assessment:	Safety assessments include AE evaluation, vital signs/physical examination, and laboratory evaluations including hematology, chemistry, 1, 25(OH)2D, 25(OH)D, PD serum and urinary assessments (see Pharmacodynamic assessment below), eCRF AE forms will be reviewed periodically to monitor the ongoing safety of the study.  An Independent Data Monitoring Committee (IDMC) will be established for this study to monitor general subject safety and specifically parameters relating to calcium metabolism, and biochemistry.
Safety endpoints:	Safety endpoints include: Serum albumin-adjusted calcium, urine calcium:creatinine ratio, phosphorus, and PTH.
Pharmacokinetic assessment:	PK assessment: to evaluate the plasma concentration of calcitriol. One single blood sample at screening and baseline to assess the endogenous levels and its variability, then a single pre-dose blood sample (C t ) will be collected at Week 4, Week 12, Week 26, and Week 30 in approximately 9 subjects 2 to 6 years and 11 months of age.
Pharmacodynamic assessment:	PD Serum (non-fasting): calcium, phosphorus, albumin (in order to calculate the serum albumin-adjusted calcium) and PTH.  PD Urine: Urine calcium and creatinine on 24-hour urine collection, whenever possible, or a urine sample after fasting for 4 hours in order to calculate Urine calcium : creatinine ratio.


Principal statistical method:
	
No inferential statistics are planned for this study.
 
The Safety Population is defined as comprising all of the subjects who have applied the study drug at least once. All data will be summarized based on the Safety Population.
 
The laboratory parameters at scheduled visits and change from Screening at post-baseline visit(s) will be summarized descriptively by visit. A shift table for lab parameters at Screening versus the Week 26/Early Termination will be provided when appropriate.
 
The categorical variables will be summarized by frequency and percentage for each response category (N, %). The continuous variables will be summarized using means, medians, minimum, maximum, and standard deviations for the data collected at each visit and the changes and percent changes from Baseline at each post-baseline visit when appropriate.
 
Treatment-emergent Adverse Events (TEAEs) will be tabulated in frequency tables by System Organ Class and Preferred Term based on the Medical Dictionary for Regulatory Activities (MedDRA). Additional summary tables will be provided for AEs that are considered serious (SAEs), related to the study drug(s), severe, AESIs, and AEs leading to discontinuation. For a given AE, a subject will be counted once even if he/she has experienced multiple episodes of that particular AE. Subgroup summaries of AEs will be provided based on gender, age group, and race when appropriate.
 
<math>C_t</math> will be submitted, after logarithmic transformation (<math>\ln</math>), to paired comparisons of Baseline and each subsequent time point. Ninety percent confidence intervals of the pairwise differences will be calculated using the Student's t statistic. The limits of the intervals will be back-transformed into exponential to obtain 90% confidence intervals of the ratios of geometric means between time points, on the original scale.
 
PK/PD relationships will be investigated by correlating <math>C_t</math> with appropriate PD parameters, using Spearman coefficient and graphical illustrations.

Sample size:
	
Sample Size Justification:          Approximately 167 subjects will be screened to enroll approximately 100 subjects into the study.

**Table 1 Clinical trial schematic**

Screening (Approximately 167 subjects)	
↓	
100 Subjects assigned to treatment with:	
	Group 1
	n= 100
Treatment	CD2027 calcitriol 3 mcg/g
Treatment Frequency	Twice daily
Treatment Duration	26 weeks

GALDERMA R&D  
 Protocol No.: RD.06.SPR.18131 V03 - 02 Dec 2015 eUS  
 Page 13 of 83

**Table 2 Schedule of Assessments**

	Clinical Trial Assessments					
	Screening Period	Treatment Period				Follow up Period
	Screening (Day -14)  V1	Baseline  (Week 0) V2	Week 4  V3	Week 12  V4	Week 26 / ET  V5	Week 30  V6
Informed Consent / Assent Form /HIPAA/PIPEDA	X					
Demographics	X					
Medical History	X					
Previous Therapies/Procedures 	X					
Physical examination and Vital signs 	X	X		X	X	
Inclusion/Exclusion Criteria	X	X 				
Urine Pregnancy Test (post menarcheal)	X	X	X	X	X	X
Record % Body Surface Area involved	X	X	X	X	X	X
Routine Blood Chemistry and Hematology	X		X	X	X	X 
Urinalysis	X		X	X	X	X
Pharmacodynamic Serum 	X	X 	X	X	X	X 
PK Blood Sampling 	X	X	X	X	X	X
Pharmacodynamic Urine 	X			X 	X 	X 
25(OH)D & 1,25 (OH)2D	X			X	X	X 
IGA	X	X	X	X	X	X
Pruritus	X	X	X	X	X	X
Drug application		Twice a day from Baseline to Week 26 V5 				
Study drug Dispensing (D) and Accountability (A) 		D	D/A	D/A	A	
Adverse Event information collection 	X	X	X	X	X	X
Concomitant Therapies/Procedures 	X	X	X	X	X	X
Moisturizer and cleanser dispensed 		X	X	X	X	
Exit Form 						X

## GALDERMA R&D

Protocol No.: RD.06.SPR.18131 V03 - 02 Dec 2015 eUS

Page 14 of 83

 Visit window of  $\pm$  3 days.

 Physical Examination to include: weight and review of systems: skin, cardiovascular, respiratory, abdomen, head and neck, musculoskeletal, neurological, lymph nodes and psychological. Height is to be evaluated at Screening visit only. Vital Signs to include: blood pressure, pulse rate

 Reconfirm that subject continues to meet inclusion/exclusion criteria.

 Total amount of Study Drug applied to involved skin should not to exceed 0.5 g/kg of body weight or 28g per day (whichever is the lower). First application to be made under the supervision of the investigator or designee. Record daily administration on dosing calendar. Dosing calendar to be checked at each visit after Baseline.

 Or at any time in case of early termination.

 The Cetaphil® Moisturizing Cream and Cetaphil® Gentle Skin Cleanser or equivalents will be provided by the Sponsor

 Events occurring after the Informed Consent Form and Assent Form (when applicable) have been signed should be recorded as Adverse Events in the eCRF

 Any therapy or medication other than study ointment will be noted on the Drugs/Therapies Form. Subjects that require a wash-out period of a prohibited therapy for >2 weeks, should be screen failed and may re-screen 1 time after completion of the washout period.

 PD Serum (non-fasting): calcium, phosphorus, albumin (in order to calculate the serum albumin-adjusted calcium) and PTH.

 PD Urine: Urine calcium and creatinine on 24-hour urine collection, whenever possible, or a urine sample after fasting for 4 hours in order to calculate Urine calcium : creatinine ratio. Subjects that are toilet-trained should be actively encouraged to complete 24-hour urine collection. A urine collection container/material will be given to the subject / subject's parent/legal guardian with the instruction to start collecting urine as of this visit and to bring the container back after the 24-hour/4-hour collection.

 Laboratory testing (full panel) will be completed at Week 30 for subjects in the PK group. For all other subjects, laboratory testing at Week 30 will be completed at Investigator's discretion.

 Subjects with suspected kidney stones should temporarily discontinue study drug and will be referred to their Primary Care Physician (PCP) for care in tandem with Sponsor consultation of the IDMC.

 The visit before: Distribute container and provide instructions for 24-hour urine collection to be started 1 day prior to Week 12 and Week 26/ET visits. The study site should contact the parent/legal guardian 48 hours prior to the visit to remind them to start the urine collection.

 Subjects may re-screen one time with written approval from the Sponsor prior to re-entry into the study.

 At Baseline, the study nurse show the subject's parents how to apply the drug.

 Visit window of  $\pm$  5 days.

 For subjects in the PK group, a single blood sample at Screening and Baseline will be taken, then a single pre-dose blood sample will be taken at Weeks 4, 12, 26 and 30, to assess the calcitriol plasma concentration. The volume of each blood sample will be 5 mL. A total volume of 30 mL will be collected during the study for PK assessment.

 Serum PD will be assessed during Baseline visit only for subjects 2 to 6 years and 11 months of age in whom PK analysis will be conducted in order to assess PK/PD relationships at Baseline for these subjects.

Unscheduled visit: When necessary and exceptionally, because of either an AE needing a specific treatment, AE leading to withdrawal from the study, laboratory result(s) that warrant further testing, or other reason.

An ongoing dialogue between subject, parent/legal guardian and investigators focusing on all aspects of the trial is encouraged. Any new information that arises in relation to the trial and that might affect the willingness of the subject and/or parent/legal guardian should be discussed. This brief discussion should be documented during each study visit.

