**5.4 Exclusion criteria**

1. Subjects with guttate psoriasis, pustular psoriasis, erythrodermic psoriasis or active infection (i.e., an infection associated with fever, swollen lymph nodes, and/or signs of localized inflammation of tissue and/or joints). *Note: allergic or vasomotor rhinitis is not exclusionary.*
2. Any newly diagnosed genetic or congenital condition, uncontrolled or serious disease, or any medical or surgical condition, that may either interfere with the interpretation of the clinical trial results, and/or put the subject at significant risk (according to Investigator's judgment) if he/she participates in the clinical trial.
3. Known or suspected allergies or sensitivities to any components of any of the study drugs (see Investigator's Brochure/Product label).
4. Female who is lactating.
5. Female who intends to conceive a child during the clinical trial.
6. Current participation in any other clinical trial of a drug or device OR participated in a clinical trial of a drug or device within 1 month prior to baseline.

7. The subject has received, applied or taken the following treatments within the specified time frame prior to the Baseline visit:

Topical treatment(s) or Procedures:	
• Corticosteroids or topical immunomodulators	2 weeks
• Tar (on areas to be treated with study drug)	2 weeks
• Vitamin D derivatives	2 weeks
• Vitamin A derivatives	2 weeks
• Intralesional steroid injections	4 weeks
Systemic treatment(s):	
• Homeopathic or herbal preparations	1 weeks
• Calcium containing products	2 weeks
• Immunomodulators and biologics known to affect psoriasis	4 weeks
• Corticosteroids or ACTH analogs	4 weeks
• Phototherapy/PUVA therapy	4 weeks
• Laser therapy	4 weeks

8. The subject or subject's parent /legal guardian is unwilling to refrain from use of prohibited medication during the clinical trial (see Section 5.5.5).
9. The subject is vulnerable (such as deprived from freedom) as defined in Section 1.61 of International Conference on Harmonisation (ICH) Guideline for Good Clinical Practice (GCP).
10. The subject has hypercalcemia (serum albumin-adjusted calcium above the upper normal range) at Screening.
11. The subject has urinary calcium:creatinine ratio above the upper normal range at Screening.
12. The subject has history or signs and symptoms of urolithiasis.
13. Subjects with known or suspected disorders of calcium metabolism.

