### 9.1.5 Safety analysis methods

No inferential statistical analysis is planned for safety endpoints of the study.

The laboratory parameters at scheduled visits and change from Screening at post-baseline visit(s) will be summarized descriptively by treatment and by visit. A shift table for lab parameters at Screening versus Week 26/ET will be provided when appropriate.

Only Treatment-emergent Adverse Events (TEAEs) will be summarized. A TEAE is defined as an AE with an onset date on or after the first application of the study drug.

TEAEs will be tabulated in frequency tables by System Organ Class and Preferred Term based on the Medical Dictionary for Regulatory Activities (MedDRA). Additional summary tables will be provided for TEAEs that are considered serious (SAEs), related to the study drug(s), and severe. TEAEs that are AESIs, as well as TEAEs leading to discontinuation will also be summarized. For a given TEAE, a subject will be counted once even if he/she has experienced multiple episodes of that particular TEAE. Subgroup summaries of TEAEs will be provided based on gender, age group, and race when appropriate.

Prior and concomitant therapies and procedures will be summarized. A prior therapy/procedure is one that ends at or before baseline; and a concomitant therapy/procedure is one starting after the baseline visit.

Extent of study drug exposure and compliance will also be summarized.

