7.3.3 Laboratory Parameters

Analysis visit will be applied for the laboratory parameter summaries.

Descriptive statistics for each laboratory parameter will be provided for scheduled visit and for the changes from Screening at each post-baseline visit. “Final” visit (Week 26 (Final)) will be defined as the last post-baseline available observation during the treatment period.

A shift table for the laboratory data at Screening versus Final will be constructed for laboratory parameters for which numeric reference ranges are available. The number of subjects below, within, and above the laboratory reference ranges at Screening versus Final will be summarized.

For each laboratory test, a complete data listing will be provided for subjects who have any laboratory results outside the reference ranges, and for subjects who have any laboratory results with clinical significance.

Plot of mean change from screening and spaghetti plot (all-subjects-in-one figure or selective individual subject figure) will be used to explore the trend of laboratory data change over the study, especially for serum albumin-adjusted calcium, urine calcium/creatinine ratio, phosphorus, PTH. Box-and-Whisker plots for PTH and Calcium/Creatinine ratio by visit will be constructed for data exploration.

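### Change from Screening in the key laboratory tests can be biased for children who stop a topical vitamin D derivative around the Screening sample, because 2-week washouts are counted back from Baseline

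*Protocol*

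**What the plan says.** **Reference value.** Protocol 9.1.5 states that "change from Screening at post-baseline visit(s) will be summarized descriptively by treatment and by visit". SAP 7.3.3 agrees: "Descriptive statistics for each laboratory parameter will be provided for scheduled visit and for the changes from Screening at each post-baseline visit", and "A shift table for the laboratory data at Screening versus Final will be constructed". The key parameters (Protocol 9.1.1.2, SAP 4.2) are albumin-adjusted calcium, urine calcium:creatinine ratio, phosphorus and PTH.

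**Washout.** Protocol 5.4, item 7, excludes a child if "The subject has received, applied or taken the following treatments within the specified time frame prior to the Baseline visit". The 2-week entries include topical "Vitamin D derivatives" and systemic "Calcium containing products". Table 2 places Screening at Day -14. Its footnote 8 says "Subjects that require a wash-out period of a prohibited therapy for >2 weeks, should be screen failed", which leaves a washout of exactly 2 weeks free to run inside the screening period.

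**Later pre-dose samples.** Under Table 2 and footnote 18, serum pharmacodynamic tests are drawn at Baseline only in the PK subset. Pharmacodynamic urine is not collected at Baseline in any subject. SAP 7.5 treats every laboratory sample before first application as Screening and, where there are several, uses the one closest to first application.

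**The protocol's view of these drugs.** Appendix 1 lists treatments it regards as acting on calcium homeostasis. Calcipotriol, calcitriol, glucocorticoids and tazarotene are among them.

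**The concern.** The washout keeps other calcium-active treatment away from the on-study values. It does not do the same for the value they are compared with. If a vitamin D derivative had already lowered PTH or raised calcium when the Screening sample was drawn, the further change on calcitriol looks smaller than it is. In a safety study that error runs in the reassuring direction. Protocol 1.3 mentions PTH abnormalities in the earlier adolescent study, so PTH is a parameter where the size of change will be read closely.

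**Working it through.** The plan gives no figure on this point to reproduce, so the check covers timing, numbers exposed, possible size and affected outputs.

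**1. Can the Screening sample fall during use?** Let G be the days from Screening to Baseline. A 2-week washout ending at Baseline allows last use on day G - 14 relative to Screening. Day -14 with a Baseline window of ±5 days (Table 2, footnote 16; Protocol section 3), read as a range for the gap, gives G from 9 to 19.

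| G (days) | G - 14 | Latest permitted use |
|---|---|---|
| 9 | -5 | 5 days before Screening |
| 14 | 0 | Screening day |
| 19 | +5 | 5 days after Screening |

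Sampling during use is possible at gaps of 14 days or more. At 9 to 13 days the product must already have stopped, but possibly only 5 to 1 days earlier.

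**2. Who lacks a later pre-dose sample?** For serum, about 100 - 9 = 91 of the 100 planned subjects. For urine, all of them. This counts subjects without a second sample, not subjects affected.

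**3. Possible size (assumptions only).** Set the untreated PTH to 1 and the on-study level to 0.70, a true 30% fall. If prior use has lowered Screening PTH by a fraction s, the apparent fall is 1 - 0.70/(1 - s):
- s = 0.10: 1 - 0.70/0.90 = 22.2%
- s = 0.20: 1 - 0.70/0.80 = 12.5%
- s = 0.30: 1 - 0.70/0.70 = 0%

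If a share f of subjects is affected, the mean change in units of the untreated level is (1 - f)(-0.30) + f(0.70 - (1 - s)) = -0.30 + f × s. The masking is f × s: 0.1 × 0.1 = 1 point, 0.3 × 0.3 = 9 points, 0.5 × 0.3 = 15 points. SAP 7.3.3 tabulates changes in value, so the percentages only give the scale.

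**4. Shift table, by parameter.**
- *Calcium and urine calcium:creatinine.* Exclusions 10 and 11 remove values above the upper normal range at Screening. Every eligible child starts at or below it, so a later high value still counts as a shift to high.
- *PTH.* Exclusion 22 names only high PTH. A low value that the investigator does not judge clinically significant (exclusion 21) can enter. Low at Screening and low at Final then shows as no shift.
- *Phosphorus.* There is no named exclusion, so the same applies to an out-of-range value.

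**5. Alerts.** Hypercalcemia and out-of-range PTH alerts (Protocol 5.6, 7.2.2.1) use absolute limits and do not depend on Screening. The 30% PTH-fall alert is relative. Section 7.2.2.1 ties it to the Baseline visit, where most subjects have no PTH sample. If Screening stood in, the true fall needed would be 1 - 0.70(1 - s), or 37%, 44% and 51% for the three values of s. The documents do not say which value is used.

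**The case against.** The strongest reply is that all this is a possibility of unknown frequency in one descriptive column. Much of that stands.

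- A reader might infer that every subject outside the PK subset has a contaminated reference. The documents do not support this: only recent users can be affected, no count is given, and early Baselines or early stopping prevent sampling during use.
- A reader might infer that calcium supplements bias the change generally. Protocol 5.5.4 requires prophylactic calcium and vitamin D to be stable for at least 4 weeks before Screening and unchanged on study, so exposure is the same at both times. Only a non-prophylactic calcium product that is stopped remains.
- A reader might infer that hypercalcemia or hypercalciuria could be hidden. It could not: the entry exclusions, absolute-limit alerts, out-of-range listings and observed values by visit all remain informative.
- For the PK subset's serum tests, the closest-sample rule in SAP 7.5 already selects the Baseline draw. A pre-dose retest in any child is handled the same way.
- The direction is not certain for every product. Topical corticosteroids and vitamin A derivatives also have 2-week washouts, and Appendix 1 lists glucocorticoids and tazarotene without saying which way they act.
- The earlier adolescent study (Protocol section 1) found no rise in systemic calcitriol over three weeks, so carry-over may be small. Section 1.3 nevertheless reports PTH abnormalities in a subset of that study.

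The reply does not remove the within-range bias in mean change, or the possible hidden shift for low PTH and phosphorus. Nor can the reported tables show how many children are involved unless someone flags them.

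**Conclusion.** The point holds in limited form. Change from Screening can be biased in children who stopped a topical vitamin D derivative, or a non-prophylactic calcium product, at or shortly before or after the Screening sample. For PTH and within-range calcium the bias is probably toward no effect. The shift-table problem is confined to low PTH and out-of-range phosphorus.

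The size is unknown. The apparent falls of 22%, 12.5% or 0% against a true 30%, and mean masking of about 1 to 15 points, rest wholly on assumed carry-over of 10% to 30% and an assumed affected share of 10% to 50%. They show that the bias could matter, not that it does. No inferential analysis is planned, so no error rate or power changes. The case for acting is that the check is cheap and uses data already recorded.

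**What to change.** **In SAP 7.3.3**, flag each reference sample (the one chosen under SAP 7.5, serum and urine separately) that was taken during, or less than 2 weeks after, use of a topical vitamin D derivative or another 2-week-washout product that the protocol lists as affecting calcium. Leave out stable prophylactic supplements. Report the number flagged by product class, and present the change and shift tables for calcium, urine calcium:creatinine, phosphorus and PTH with and without the flagged subjects. State a rule for incomplete stop dates.

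No new data are needed: Protocol 5.5.1 and 5.5.3 already require these therapies to be recorded, and SAP 7.2.3 already works from stop dates. The cost is SAP wording and one sensitivity table with somewhat fewer subjects.

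**In the protocol**, reconcile the calcium washout in exclusion 7 (also prohibited on study through section 5.5.5) with the prophylactic calcium allowed in exclusion 17 and section 5.5.4. The flag needs a clear definition of which calcium products count.

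Moving the Screening draw to the end of washout is not recommended. Results must be available before Baseline (Protocol 7.2.2), so children would stop therapy before their laboratory eligibility is known, with about 40% screen failure expected. A separate reference rule for the PK subset is unnecessary, since SAP 7.5 already gives it.
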